7.1.3. Data and biosample retention

Archiving will be authorised by the Sponsor following submission of the end of study report. Investigators are responsible for the secure archiving of essential trial documents and the trial database as per their trust policy. All essential documents will be archived for 5 years after completion of trial. Destruction of essential documents will require authorisation from the Sponsor.

Biosamples will be used for data analysis as specified and destroyed no later than 5 years after study closure, unless local national regulations specifically allow longer retention times (e.g. UK).

7.1.4. Clinical quality assurance

The trial management group (TMG), consisting of the coordinating investigator, site investigators and experts from relevant specialties (if required) will meet routinely in accordance with the TMG terms of reference, to discuss and address any concerns regarding the conduct of the study. The TMG will be consulted for appropriate review and adjudication of adverse events. Please refer to the TMG Charter for further details.

8. AMENDMENTS TO THE CIP

Amendments to this CIP may be necessary to protect the safety of the patients and integrity of the data. In collaboration with the Investigator(s), the CIP amendments will be documented and submitted for ethical and regulatory approval prior to implementation. All changes will be evaluated for impact per Sponsor SOPs. Amendments will be considered implemented after all ethical and regulatory approvals are received and all key sponsor and site staff has been trained. This process does not affect the individual clinician's responsibility to take immediate action if thought necessary to protect the health and interest of individual patients.

Clinical Investigation Plan	CIP YAQ-002	Version: 7.0 10 October 2019
-----------------------------	-------------	------------------------------

The Prismaflex utilizes certain software to appropriately run the pumps according to specific settings. Per the user manual of oXiris and septeX a software version 4.0 or higher is to be used. For the DIALIVE study, in Austria a software version 8.1 only will be allowed.

9. DEVIATIONS FROM CLINICAL INVESTIGATION PLAN

A deviation is either a violation of the conditions and principles of GCP in connection with that trial; or the CIP relating to that trial, as amended from time to time.

The Investigator shall not deviate from this CIP except in situations that affect the subject's rights, safety and well-being, or the scientific integrity of the clinical investigation.

9.1. Procedures for recording, reporting and analysing CIP deviations.

Any deviations form the CIP that occur must be documented on the deviation log and maintained by the study site throughout the duration of the Investigation. Deviations will be submitted to Data Management so they maybe included in the analysis.

9.2. Notification requirements and time frames.

Requests for deviations by the investigator will be responded to by the Sponsor within 48 hours of receipt.

9.3. Corrective and preventive actions and principal investigator disgualification criteria.

Refer to the Yaqrit Risk-based Monitoring Plan, for corrective and preventative actions and principal investigator disqualification criteria.

10. DEVICE ACCOUNTABILITY

The DIALIVE system has been assessed against the Medical Devices Directive 93/42/EEC (MDDs) Essential Requirement (ERs) aspects as listed in Annex I of the IB. It is concluded that DIALIVE complies with the MDD ERs except for those aspects that are the subject of this investigation:

Essential Requirements 1 and 3 relating to patient safety and 6 relating to determination of side effects

The quality of the haemofilters used in DIALIVE is assured by design and production certified compliant with MDD Annex II (Full Quality Assurance System) and ISO 13485 Quality Management Systems for Medical Devices – System requirements for regulatory purposes.

The same applies for the inter-dialyser connection tubing.

The commercially available filters and connecting tube (Device) will be purchased directly from the suppliers and repackaged by Yaqrit Ltd into a box labeled "exclusively for clinical investigation". The sterility of all component parts will not be altered in any way. Yaqrit Ltd will release and distribute the required number of devices to the sites ready for use. Each device will be assigned a unique device code to ensure full traceability once sent to sites. The sponsor will

Clinical Investigation Plan CIP YAQ-002 Version: 7.0 10 0	October 2019
---	--------------

maintain a master list of all devices. The device shall be stored according to the storage conditions listed in the approved IB.

Access to the DIALIVE device shall be controlled and the device shall only be used in the clinical investigation according to this CIP. The Sponsor will maintain records to document the physical location of all devices from shipment to sites to destruction. The instructions for use are detailed in the IB. DIALIVE treatment will be delivered by either (a) Trained study specific staff provided by Yaqrit Limited or (b) Site specific staff that have been specifically trained in the use of DIALIVE and signed training logs will be maintained in the Trial Master file.

Each site will maintain accountability records from receipt of the devices through to its use on a per patient basis and destruction following each treatment to ensure a full audit trail is maintained. This shall include the following information:

- a) the date of receipt,
- b) identification of each investigational device (batch number/serial number or unique code),
- c) the expiry date, if applicable,
- d) the date or dates of use.
- e) subject identification,
- f) date on which the investigational device was returned/explanted from subject, if applicable, and
- g) the date of return of unused, expired or malfunctioning investigational devices, if applicable.

11. STATEMENTS OF COMPLIANCE

11.1. Declaration of Helsinki, International Standards and national regulations

The clinical investigation shall be conducted in accordance with the ethical principles of the Declaration of Helsinki, MDD 93/42/EEC, ISO 14155:2011 and all other applicable national regulations.

11.2. Approvals

The clinical investigation shall not commence at the site until ethics and regulatory approval and any institutional approval (as applicable) is received. All additional requirements imposed by the ethics committees and/or regulatory authority will be followed. No device will be release to site until all applicable approvals have been verified and the site initiation has been undertaken/scheduled.

11.3. Insurance

The Sponsor will maintain appropriate trial insurance for the clinical investigation as detailed in the Clinical Investigation Agreement(s).

Clinical Investigation Plan	CIP YAQ-002	Version: 7.0 10 October 2019
-----------------------------	-------------	------------------------------

12 INFORMED CONSENT PROCESS

Fully informed consent will be obtained at the initial screening visit. It will be the responsibility of the Investigator, or designee (on the delegation log) to obtain written informed consent from each subject prior to participation in the trial, following adequate explanation of the aims, methods, anticipated benefits and potential hazards of the study. The inclusion of patients with reduced capacity or who are unconscious (HE grade 3 or 4) is restricted to the approval based on local and / or national legislation. In different European countries, different rules apply. The applicable approach will be documented and applied according to the local or national Ethics Committee guidelines, recommendations or obligations.

Two approaches need to be considered.

A. Patient is conscious at start of enrollment process but might be at jeopardy to lose capacity as decided by the treating investigator. To provide additional protection of subjects, each subject will be offered the option – in line with local and national regulations – to nominate a consultee/representative at the point of consent who, should the patient loose capacity during the study, will act under their presumed wishes and ensure any study intervention conducted will have the consent of the consultee/representative. If a consultee/representative is appointed, he/she must have agreed to act in this capacity before the patient is randomized (i.e. during the screening phase) and this must be documented in the medical notes by site. Where verbal agreement has been initially sought, the site must ensure the Patient Informed Consent Form is co-signed and filed in the site file as soon as is practicable but not later than patient discharge from hospital. Where a patient does not have a consultee/representative (family member, legal representative) and in case he/she would prefer to have one appointed, a professional consultee/representative (independent of the study) will be offered to the patient. The consultee/representative will not undertake any decision making on behalf of the patient unless they are deemed to have lost capacity based on medical assessment.

B. Patient is unconscious at start of enrollment process. As this constitutes a 'vulnerable patient' per the definition of the ISO 14155, special care is to be provided that all local and national regulations are implemented. Inclusion of this kind of vulnerable patients might be prohibited, while in other countries or centers tolerated under specific conditions. These conditions might be linked, but are not restricted to the optimal treatment of the patient by the investigator and/or to the release of the clinical data which need to be approved at study end by either the patient's or the legal representative's consent, OR the upfront written consent by a legal representative, identified and approved per the local/national regulations

"Adequate time" will be given for consideration by the patient before taking part. The investigator, or designee, will record when the Informed Consent documents has been given to the patient. The Investigator or designee will explain the patients are under no obligation to enter the trial and that they can withdraw at any time during the trial, without having to give a reason. The patient will be given the opportunity to ask questions prior to signing the consent. No clinical trial procedures will be conducted prior to obtaining appropriate consent. A copy of the signed Informed Consent Form (ICF) will be given to the participant. The original signed form will be retained at the study site and a copy placed in the medical notes. If new safety information results in significant changes in the risk/benefit assessment, the consent form will be reviewed and updated if necessary and subjects will be re-consented as appropriate within the time limits of the study.

As this is not an emergency treatment, no patients shall be enrolled into the study without full informed consent following the local/national legislation. Once a patient provided appropriate consent, this consent remains valid until study completion, withdrawal or exclusion.

Each Investigator will maintain a log of all subjects enrolled into the trial, to ensure assigned trial codes and names can be linked. This will be retained at each site.

Clinical Investigation Plan CIP YAQ-002 Version: 7.0 10 October 20	19
--	----

12. Adverse events, adverse device effects and device deficiencies

12.1. The definitions are compliant with ISO 14155 and MEDDEV Guidance 2.7.1 rev 3

Term	Definition
Adverse Event (AE)	Any untoward medical occurrence, unintended disease or injury, or untoward clinical signs (including abnormal laboratory findings) in subjects, users or other persons, whether or not related to the investigational medical device. Note 1: This definition includes events related to the investigational medical device or the comparator Note 2: This definition includes events related to the procedures involved Note 3: For users or other persons, this definition is restricted to events related to investigational medical devices
Adverse Device Effect (ADE)	Adverse Event related to the use of an investigational device. Note 1: This definition includes AEs resulting from insufficient or inadequate instructions for use, deployment, implantation, installation, or operation, or any malfunction of the investigational device Note 2: This definition includes any event resulting from use error or from intentional misuse of the investigational medical device
Serious Adverse Event (SAE)	 Any adverse event that: Led to death, injury or permanent impairment to a body structure or a body function Led to serious deterioration in the health of the subject, that either resulted in a life-threatening illness or injury, or a permanent impairment of a body structure or a body function, or in-patient or prolonged hospitialization, or in medical or surgical intervention to prevent life-threatening illness Led to foetal distress, foetal death or a congenital anomaly or birth defect Planned hospitalization for a pre-existing condition or a procedure required by the CIP, without a serious deterioration in health is NOT considered a SAE.
Serious Adverse Device Effect (SADE)	An ADE that has resulted in any of the consequences characteristic of an SAE
Unanticipated Serious Adverse Device Effect (USADE)	An SADE, which by its nature, incidence, severity or outcome has not been identified in the current version of the risk analysis report.
Device Deficiency (DD)	Inadequately of a medical device with respect to its identity, quality, durability, reliability, safety or performance. Note 1: this includes malfunctions, use errors, and inadequate labeling

An adverse event does not include:

Clinical Investigation Plan	CIP YAQ-002	Version: 7.0 10 October 2019
-----------------------------	-------------	------------------------------

- Medical or surgical procedures; the condition that leads to the procedure is an adverse event.
- Pre-existing disease, conditions, or laboratory abnormalities present at the start of the study that do not worsen in frequency or intensity.
- Situations where an untoward medical occurrence has not occurred (e.g., hospitalizations for cosmetic or elective surgery or social/convenience admissions);
- The disease being studied or signs/symptoms associated with the disease unless more severe than expected for the subject's condition.
 - Expected post-operative course (see section 3)
- 12.2. Reporting requirements and timelines
- The SAE reporting form in appendix 1 of the MEDDEV guidance will be used unless national/local requirements specify a different reporting requirement.

In line with MEDDEV guidance 2.7/3 rev 3 May 2015 and Annex X section 2.3.5 of the MDD⁴⁰

Term	Reporter	Reported to	Reporting Timeline from awareness of the event
Adverse Event (AE)	Investigator	Sponsor/CRO	As soon as reasonably possible
Adverse Device Effect (ADE)	Investigator	Sponsor/CRO	As soon as reasonably possible
	Investigator	Sponsor/CRO	Immediately, not later than 3 calendar days after site awareness of event
Device Deficiency (DD)	Sponsor/CRO	CA/Ethics Committee	Immediately but no later than 2 calendar days if the event may have led to an SAE if; • suitable action had not taken • intervention had not been made • if circumstances had been less fortunate
	Investigator	Sponsor/CRO	Immediately, not later than 3 calendar days after site awareness of event
Serious Adverse Event (SAE), Serious Adverse Device Effect (SADE), Unanticipated Serious Adverse Device Effect (USADE)	Sponsor/CRO	CA/Ethics Committee	Immediately but not later than 2 calendar days of sponsor becoming aware of event if event indicates an imminent risk of death, serious injury, or serious illness and that requires prompt remedial action for other patients, users or persons, or a new finding to it For all other events Immediately but not later than 7 calendar days of sponsor becoming aware of event
New findings/updates in relation to already reported events	Sponsor/CRO	CA/Ethics Committee	Immediately but not later than 7 calendar days of sponsor becoming aware of event

 $^{^{\}rm 40}$ Special national requirements might apply and will be implemented

Clinical Investigation Plan CIP YAQ-002 Version: 7.0 10 October 20	19
--	----

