The Hepalbin[™]-Adsorbent is a nano-structured carbon filter that removes up to 95% of the industrial stabilisers octonoic acid (caprylate) and N-acetyltryptophanate from commercially available pharmaceutical albumin preparations. These stabilisers are associated with the binding sites of albumin, thus reducing albumin functionality and binding capacity. While in healthy individuals, these stabilisers are metabolized by the liver and have a very short half-life, this is significantly prolonged in liver disease potentially causing accumulation of these materials. The use of Hepalbin[™]-Adsorbent for albumin transfusion indicated that there may be clinical benefit to stabilizer removal in patients with decompensated liver disease in a small controlled study [16].

-

SepteX and oXiris filters are the brandnames of the filters and have no further model specification.

⁸ In the majority of hospitals most recent versions of both Prismaflex and software are available. In Austria the Model ref: 60 23014700 can be in used in Graz; the software version installed is version 8.1

Clinical Investigation Plan	CIP YAQ-002	Version: 7.0 10 October 2019
-----------------------------	-------------	------------------------------

2.2 Definitions.

Screen failures:

- The patient does not meet one or more criteria, which are assessed after the patient (and/or consultee if applicable) signed the Informed Consent; patient can re-enter the study later if at that moment all inclusion criteria and no exclusion criteria are met. Patient informed consent remains valid until end of the study or until withdrawal from the study.
- 2. Patient who did not start dialysis before the end of DAY 1 if randomized to the DIALIVE treatment arm, is considered a screen failure; such a patient does not have to resign a consent form, but can re-enter the study via de novo demonstration of compliance with the in- and exclusion criteria.

Patient withdrawal: a patient (or the consultee if applicable) can withdraw consent at any time. No further clinical data can be collected as of that moment; the data collected prior to that moment, remain part of the clinical study.

Patient exclusion: a patient is considered excluded from the study (and from re-entering into the study):

- 1. Upon demonstration of more than 2 interuptions of more than 24 hrs between subsequent dialysis sessions and within the first 10 day time period after randomization (DIALIVE arm);

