- 2. If the clinical condition of a patient meets one or more study stopping criteria.

Patients considered to be a 'screen failure' or 'excluded' will remain in study for a minimum follow up period of 28 days.

Standard definitions: definitions for DIALIVE organ failure and ACLF grading per the CLIF-C OF scoring system, Lille score, and others, are given in Appendix 1-2.

Hepatic Encephalopathy (HE): determination of HE as part of ACLF grading will be based upon clinical assessment and graded as per the West Haven criteria. However, if there is ambiguity or observer variability, an EEG may be sought by the PI for supportive evidence. This is particularly relevant for grade 1 HE which may not be consistenly reproducible using the West Haven criteria, and as such is now included as part of the covert HE spectrum along with minimal HE often requiring psychometric tests or EEG for diagnosis

Specific therapy such as corticosteroids for alcoholic hepatitis can be used if a patient is already within the study and these have not been trialed previously and as long as clinical justification and rationale is clearly documented. This applies to patients in both SOC and the DIALIVE arm. For other indications of steroid use such as potential relative adrenal insufficiency, it should precede a short synacthen test, particularly in patients who are haemodynamically stable, to establish this diagnosis.

Standard of Care (SOC) is defined as the standard medical and nursing management of patients with ACLF Grades 1 and 2 as per local practices. Medical intervention is to be guided by the treating physician taking into account the overall clinical picture, precipitating event, and the nature and severity of organ dysfunction. The interventions may include (but not limited to) the supportive management with fluid therapy, including albumin therapy where indicated, antibiotics for suspected or confirmed infections, nutrition, bowel management, thromboprohylaxis, and organ system support including the use of terlipressin as splanchnic vasopressor and for cardiovascular support where indicated, oxygen and non-invasive respiratory support, laxatives and non-absorbable antibiotics for hepatic encephalopathy, and dialytic therapy for renal failure. SOC may also include urgent liver transplantation as per local practices.

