5.1.3 Secondary End Points

To evaluate the performance of the DIALIVE in patients with ACLF. This is measured by;

Change in Plasma endotoxin level (endotoxin activity and concentration) between;

D1, D3, D5 and D10 across SOC arm $\,$

D1, D3, D5 and D10 across DIALIVE arm

_

¹⁰ In case a patient's treatment is discontinued, the follow up period will remain 28 days from the moment of randomization.

Clinical Investigation Plan	CIP YAQ-002	Version: 7.0 10 October 2019
-----------------------------	-------------	------------------------------

Start and end of a treatment session (on D1, D2 and D3) with DIALIVE D1,D3, D5 and D10 between SOC and DIALIVE arms for patients presenting with the same grades of ACLF (i.e. Grade 1 ALCF compared with Grade 1 ACLF)

Target-Value (TV): 40% reduction; Acceptable-Value (AV): 20% reduction at end of treatment cycle.

• Change in Albumin function (Human non-mercapt albumin -2 (HNA-2) / Human marcapt albumin (HMA) ratio:

D1, D3, D5 and D10 across SOC arm
D1,D3, D5 and D10 across DIALIVE arm
Start and end of a treatment session (on D1, D2, D3) with DIALIVE
D1,D3, D5 and D10 between SOC and DIALIVE arms for patients presenting with the same grades of ACLF (i.e. Grade 1 ALCF compared with Grade 1 ACLF)

TV: 40% reduction; AV: 20% reduction at end of treatment cycle.

- Mortality: 28-days and 90 days
- Change in ACLF Grade
- Change in CLIF-ACLF score
- Improvement in individual organ function: Brain (HE), Kidney (creatinine), CVS (mean arterial pressure), Pulmonary (P/F ratio, or S/F if patient is not intubated), Liver (serum bilirubin) and coagulation (INR and platelets).
- Status at ICU and Hospital Discharge (including discharge to a hospice for palliative care).
- Lengths of stay in ICU and Hospital at D28 and D90
- ICU and Hospital re-admissions with another episode of ACLF up to 3 months after randomisation.

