5.1.6. Equipment to be used for assessing the clinical investigation

All equipment except for the DIALIVE device, the EAA luminometer for endotoxin analysis, and the Primsmaflex platform¹¹ will be the property of the Investigator(s) and/or institutions and maintained and calibrated according to institutional guidelines. Records of maintenance and calibration will be made available at the Sponsor's request.

5.1.7. Replacement of subjects.

30 evaluable patients will be recruited across all sites to receive either treatment using the DIALIVE or SOC. Screen failures will be replaced to achieve an even balance in each cohort. The patient numbers will be increased and replaced if there are dropouts during the treatment period to allow 30 evaluable patients to be included. Dropouts can be i) patients who withdraw their consent, ii) patients who are considered 'not evaluable' because of an incomplete dialysis cycle (for DIALIVE patients) or iii) if a patient dies in the 10-day period following randomization to the SOC-arm, or iv) patients who are excluded based on a stopping rule.

A dropout rate of 17% is anticipated on the basis of observations made during execution of this study in the first 2 cohorts of patients. Patients who drop-out for reasons of an incomplete dialysis cycle are followed up for a duration of 28 days post-randomization.

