5.3.3. Criteria and procedures for subject withdrawal or discontinuation

Other than those required for liver dialysis, no additional Investigation or interventions are expected over and above the routine SOC, which the patient will continue to receive. It is anticipated, therefore, that all subjects will continue to be highly compliant with the CIP study procedures. Non-compliance with the CIP study procedures will be documented by the investigator and reported to the Sponsor as agreed. Persistent non-compliance may lead to be withdrawn of the patient from the study.

The participant may, however, voluntarily choose to withdraw from the study at any time for any reason. This will not in any way affect their routine care. If the participant loses capacity during the study, the legal representative (if appointed) also has the right to withdraw the participant in this instance, acting on the presumed wishes of the participant.

The investigator also has the right to withdraw a patient at any time due to failure to follow CIP, administrative, safety or other reason. Stopping rules (for the study and for the DIALIVE treatment) have been developed as follows:

- A) Rules for discontinuing DIALIVE therapy during a treatment session, based on safety grounds
 - a. Persistent shock (MAP < 65mmHg or < 90% pre-treatment value, whichever is higher) for > 2 hrs with features of tissue hypoperfusion, unresposive to volume resuscitation and/or low dose noradrenaline (0.1µg/kg/min). Treatment can be restarted once haemodynamic stability is restored.
 - b. Deteriorating respiratory failure as defined by worsening PaO₂/FiO₂ to < 200 mmHg (27 kPa) and SaO₂/FiO₂ to < 214. Treatment can be recommenced following a 12 hour recovery period.
 - c. Disseminated Intravascular Coagulation (DIC). Thrombocytopenia alone (to below exclusion criterion threshold) without evidence of DIC is not a stopping rule. Platelet treatment should be considered in this case.
 - d. Progression to more than 3 organ failures

Clinical Investigation Plan CIP YAQ-002 Version: 7.0 10 October 20	19
--	----

- e. In the opinion of the PI, the treatment is unsafe to continue
- B) Study stopping rules for patients randomized to either the SOC or the DIALIVE arm
 - a. Withdrawal of patient consent by the patient (or if applicable the appointed respresentative, where the patient were to lose capacity during this process).

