 - b. Following review of safety data by the DSMB if they wish to stop the study on safety grounds

The reasons for screen failure or withdrawal shall be documented in the eCRFs and in the patient notes. If a withdrawal is on the grounds of safety the Investigator will seek permission from the patient, or legal representative as appropriate, to follow up his/her status outside of the Investigation, but at least until resolution or full clarification of the adverse event.

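### Section 12 ends consent at exclusion, and 5.3.3 moves follow-up after a safety withdrawal outside the study; both conflict with the 28-day in-study follow-up set elsewhere in the protocol

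*Protocol*

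**What the plan says.** **Consent.** Section 12 (Informed consent process) says: "Once a patient provided appropriate consent, this consent remains valid until study completion, withdrawal or exclusion". Section 2.2 says: "Patient informed consent remains valid until end of the study or until withdrawal from the study". Exclusion is not on that second list.

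**Excluded patients.** Section 2.2 defines exclusion by two routes: repeated dialysis interruptions (marked DIALIVE arm), or a clinical condition that meets a study stopping criterion. A second failed session in the 10-day window also leads to exclusion. Section 2.2 then says: "Patients considered to be a 'screen failure' or 'excluded' will remain in study for a minimum follow up period of 28 days". Section 5.1.7 adds: "Patients who drop-out for reasons of an incomplete dialysis cycle are followed up for a duration of 28 days post-randomization".

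**Discontinued treatment.** Footnote 10 is attached to the endpoint of DIALIVE discontinuation due to a SADE. It says: "In case a patient's treatment is discontinued, the follow up period will remain 28 days from the moment of randomization".

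**Withdrawal by the investigator.** Section 5.3.3 says: "The investigator also has the right to withdraw a patient at any time due to failure to follow CIP, administrative, safety or other reason". If a withdrawal is on safety grounds, "the Investigator will seek permission from the patient, or legal representative as appropriate, to follow up his/her status outside of the Investigation".

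**Capture and analysis.** Section 12.4.1 makes deaths during study participation reportable as SAEs. Section 6 analyses available data only, without imputation.

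**The concern.** Exclusion is a defined term, so its appearance in the consent sentence has a specific effect: the section 12 consent stops at the point where 2.2 starts a period of in-study follow-up. A site reading section 12 may conclude that it cannot record that follow-up as study data. A site reading 2.2 will record it.

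Section 5.3.3 raises a related problem. A patient withdrawn for safety by the investigator, without having withdrawn consent, is to be followed outside the investigation and only after new permission. Sections 12 (Informed consent process) and 13 recognise that these patients may lose capacity, so permission may be hard to obtain when it is needed.

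The data at stake are the percentage of subjects with an SAE from Day 1 to Day 10, which is a primary endpoint, and 28-day mortality, which is secondary. The analysis is descriptive, so these percentages are the result. Events that are never collected cannot be restored at the analysis stage.

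**Working it through.** The plan states no figure on this point. The check compares the rules and then illustrates the scale.

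**Step 1. Which rule applies to which patient**

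| How the patient leaves | Rules that keep data in the study | Rules that may take data out |
|---|---|---|
| Excluded for failed or interrupted sessions | 2.2 (at least 28 days, in study); 5.1.7 (28 days) | Section 12: consent ends at exclusion |
| Excluded on a stopping criterion | 2.2 (at least 28 days, in study) | Section 12, as above |
| Treatment discontinued for a SADE, patient still in study | Footnote 10 (28 days) | None |
| Withdrawn by the investigator for safety | None names this case; 2.2 applies if it counts as exclusion on a stopping criterion | 5.3.3: new permission, outside the investigation |
| Withdraws own consent | None | 2.2 and section 12 agree that collection stops |

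Rows 1 and 2 are a direct contradiction. Row 4 is a conflict by overlap: 2.2 has no separate category for a safety withdrawal by the investigator. Rows 3 and 5 are not in conflict.

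**Step 2. An example.** A DIALIVE patient is excluded after a second failed session on Day 3, has an SAE on Day 6 and dies on Day 20. Under 2.2 and 5.1.7 both events fall inside study follow-up. Under section 12 the consent lapsed on Day 3.

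**Step 3. Exposure by arm.** Session-based exclusion can occur only in the DIALIVE arm. The stopping-criterion route is not restricted by arm, and section 6 summarises discontinuations for such criteria by treatment arm. Appendix 7 reports 2 of 8 DIALIVE patients non-evaluable (25%; exact 95% interval 3% to 65%) and mentions none among 6 SOC patients. Fisher's exact p is 0.47, so these counts do not establish an imbalance. The difference in exposure rests on the rules.

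**Step 4. Scale for the SAE endpoint.** Assumption: 15 to 20 treated DIALIVE patients. The lower figure is 5 cohorts × 3 = 15; the upper is 15 × 8/6 = 20, if the early ratio of enrolled to evaluable patients persists. If a patient stays in the denominator but the only SAE in the window is not recorded:

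- one patient: 1/20 = 5.0 points, 1/15 = 6.7 points;
- two patients: 2/20 = 10 points, 2/15 = 13.3 points.

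**Step 5. Scale for 28-day mortality.** Assumption: 15 completers at 32% mortality and 5 excluded patients, whose mortality varies over the range that section 2.7 quotes by ACLF grade.

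- Excluded at 78%: true value (15 × 0.32 + 5 × 0.78)/20 = 43.5%. It reads 32% if the excluded drop out of the data and 4.8/20 = 24% if they are counted as alive.
- Excluded at 32%: true value 32%. It reads 32% if they drop out and 24% if counted as alive.
- Excluded at 22%: true value (4.8 + 1.1)/20 = 29.5%. It reads 32% if they drop out and 24% if counted as alive.

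The size, and even the direction, depends on who is excluded and how the missing outcome is handled.

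**The case against.** The best defence is that the operative rules already keep these patients. Sections 2.2 and 5.1.7 and footnote 10 all set 28 days. Section 5.1.5 includes all treated subjects in the analyses, any duration of exposure counts as treatment, and section 12.5 records all AEs from the point of consent. Against them stands one general consent sentence, which may have been meant only to deal with re-entry without re-signing; the consent sentence in 2.2 itself sits in the screen-failure paragraph. The DSMB report does count the two non-evaluable DIALIVE patients and describes both early DIALIVE deaths. This stands as evidence that no loss has been shown. It does not remove the contradiction: the 2.2 rule for excluded patients is independent of the re-entry text, and section 12 states an end of consent without that limit.

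A reader might infer more than the text supports:

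- *That 5.3.3 limits follow-up to one adverse event.* It does not. The permission sought is "to follow up his/her status outside of the Investigation, but at least until resolution or full clarification of the adverse event", which sets a minimum.
- *That footnote 10 flatly contradicts 5.3.3.* The footnote concerns discontinued treatment, and 5.3.3 concerns withdrawal. The safety stops in 5.3.3 A act on therapy during a session, and two expressly allow a restart. The amendment history also describes the follow-up sentence as serving patients who withdraw after a serious device or procedure event, so it may have been meant to add follow-up. The remaining gap is a study withdrawal initiated by the investigator on safety grounds.
- *That only DIALIVE patients are exposed, or that the device is shown to look safer than it is.* Step 3 does not support the first. The second would need lost events, and none is documented.

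**Conclusion.** The point holds as an inconsistency in the protocol. Section 12 contradicts 2.2 directly on whether consent survives exclusion, and it undercuts the 28-day follow-up in 5.1.7. Section 5.3.3 leaves unclear whether a patient withdrawn by the investigator for safety remains a source of study data. A site following either text as written could omit SAEs and deaths that belong to the Day 1 to 10 and 28-day endpoints, with greater exposure in the DIALIVE arm.

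The size of any bias is unknown. The figure of 5 to 6.7 points per patient assumes 15 to 20 treated DIALIVE patients, an only SAE that falls after departure, and a site that does not record it. The documents give no count of such patients. The study tests no hypothesis, so no inference is invalidated. The matter deserves correction because safety is the primary objective and uncollected data cannot be recovered later.

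**What to change.** 1. In section 12 (Informed consent process), delete exclusion from the consent sentence so that it matches 2.2. Check the consent form for the same wording, subject to national rules. The form was not available for this review.
2. In 5.3.3, state that, unless consent itself is withdrawn, a patient withdrawn by the investigator stays in the investigation for SAE and survival collection for at least the 28 days set in 2.2. Withdrawal, as an end of consent in 2.2 and section 12, then means withdrawal of consent.
3. State that SAEs and deaths collected in this way count in the Day 1 to 10 SAE and 28-day mortality endpoints.

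The ban in 2.2 on further data collection needs no change, because it already applies only to withdrawn consent. Following excluded patients in cohorts 4 and 5 to Day 90 would be a new requirement and is not needed to reconcile the text.

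The cost is a few sentences in the next amendment and, if the form needs it, one line there. For excluded patients the 28-day follow-up is already in the protocol. For investigator withdrawals the change settles a rule that is now unclear.
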